7.1 Adverse Event of Special Interest - Myalgia

Myalgia has been reported as the dose limiting toxicity across the oncology studies. The incidence of myalgia appears to be dose dependent and cumulative. However, it has been reported in subjects receiving doses as low as $5\mu\text{g}/\text{m}^2$. The myalgia has been investigated in some studies but not all. No increase in muscle enzymes were found in the cases investigated. EMG was abnormal in one subject who received $65\mu\text{g}/\text{m}^2$ and suggested a patchy myositis. An MRI done in another subject was normal.

For all cases of myalgia despite the severity, a narrative will be created documenting onset, severity, treatment and outcome. Muscle enzymes, CPK, will be collected for all cases and compared to baseline values. Additional investigations are at the discretion of the investigator.

7.2 Definition of Serious Adverse Event

An SAE is any untoward medical occurrence that fulfills any of the following criteria:

- Results in death (fatal)
- Is life threatening (an event is considered "life threatening" if, in the view of either the investigator or sponsor, its occurrence placed the subject at immediate risk of death. It does not include an AE that, had it occurred in a more severe form, might have caused death).
- Requires in-patient hospitalization or prolongation of existing hospitalization
- Results in a persistent or significant disability/incapacity

- Is a congenital anomaly/birth defect
or
- Is an important medical event (events that may not result in death, be immediately life threatening or require hospitalization; may be considered serious when based upon appropriate medical judgment, they jeopardize the subject and may require medical or surgical intervention to prevent any of the outcomes listed above. Examples include; allergic bronchospasm requiring intensive treatment in an emergency room or at home, convulsions that do not result in hospitalization, or the development of drug dependency or drug abuse.

The following situations may not, by themselves, constitute sufficient grounds to be considered as an SAE:

- Hospitalization solely for a diagnostic purpose, even if related to an AE,
- Elective hospitalization for an intervention planned before the subject enrollment in the study
- Admission to a day care facility or sleeping laboratory

7.3 Assessment of Intensity

Severity is a clinical determination of the intensity of an AE and will be determined by the PI based on the following classification criteria for all AEs occurring during the clinical study:

Mild - Awareness of signs or symptom, but easily tolerated, may require additional therapy

Moderate - Discomfort, enough to cause interference with usual activity and to require intervention or additional therapies

Severe - Incapacitating with inability to work or perform usual activity

Note: It should be noted that a severe AE need not be serious in nature and that an SAE is not, by definition, severe. Regardless of intensity, all SAEs and significant events must be reported.

7.4 Relationship to Study Drug

The causal relationship between the investigational drug and each AE will be determined by the PI based on his/her medical judgment in consideration of all relevant factors, including pattern of reaction, temporal relationship, positive, concomitant medication, co-existing diseases, and relevant medical history. The PI will classify every AE according to its relationship to study drug or trial-related procedures. The categories according to World Health Organization guidelines are listed in the following Table

7.5 Table 2 Relationship of AE to Study Drug or Trial-Related Procedures

Rating	Classification	Definition
1	Probable	An AE that: 
 • Occurs at a reasonable time interval after administration of the study drug; • Follows a known response pattern to the study drug and; • Cannot be reasonably explained by the known characteristics of the subject's clinical state or by other therapies.
2	Possible	An AE that: 
 • Occurs at a reasonable time interval after administration of the study drug; • Follows a known response pattern to the study drug, but; • Could have been produced by the subject's clinical state or by other therapies. •
3	Unlikely*	
 • An AE for which sufficient information exists to indicate that the etiology is unrelated to the study drug; • Another etiology is specified.

*If the AE is classified as unlikely, the PI should provide a likely cause, other illness, concomitant medication, or other.

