7.5.1 Unexpected Adverse Event

An AE is considered “unexpected” if it is not listed in the Investigator’s Brochure (IB) or is not listed at the specificity or severity that has been observed. Unexpected refers to AEs that are mentioned in the IB as occurring with a class of drugs or as anticipated from the pharmacological properties of the drug, but are not specifically mentioned as occurring with the particular drug under investigation. However, an event that is more specific or more severe than described in the IB will be considered unexpected.

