7.6.2 Reporting to Regulatory Authorities

The PI, or designee, is responsible for informing the Institutional Review Board (IRB) of any unexpected SAEs, as well as any additional SAEs according to the IRB's policy.

Any SAE that is serious, suspected to be related to investigational study drug and unexpected (SUSAR), will be promptly reported to regulatory authorities by the Sponsor according to expedited reporting requirements. Subsequent relevant information after the initial submission of the (IND) Safety Report to the regulatory authorities will be submitted in a follow-up IND Safety Report to the regulatory authorities in the expedited period by the Sponsor.

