8.3.1 Adverse Events

Adverse events will be coded using the most recent version of Medical Dictionary for Regulatory Activities (MedDRA). Treatment Emergent AE's (TEAE) are defined as events with an onset on or after the first randomized treatment. TEAEs will be summarized by treatment group, System Organ Class, and preferred term. The following TEAE summaries will be provided:

- Overall (*i.e.*, regardless of severity or relationship to treatment)
- By severity grade (mild, moderate, severe, life threatening or death for SAEs)
 - By relationship to clinical trial treatment (definitely related, probably related, possibly related, unlikely related, unrelated)

Unless otherwise specified, at each level of subject summarization, a subject will be counted only once. If there is more than one occurrence of an event, the event of the worst severity or the worst-case relationship category will be summarized.

In addition, separate summaries of serious adverse events, and adverse events resulting in discontinuation of study treatment will be presented.

AEs leading to premature discontinuation of clinical trial treatment, AEs that lead to study discontinuation, AEs that lead to death and Serious Adverse Events (SAEs) will also be summarized by treatment group and relationship.

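### Table 2 makes a known response pattern a condition of both drug-related ratings, so a new reaction with no other cause fits no rating, and its three levels do not match the five to be tabulated

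*Protocol*

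**What the plan says.** Protocol 7.4 has the investigator determine causality by medical judgment, weighing several factors, of which pattern of reaction is one. It then requires every AE to be classified with the categories of Table 2 (Protocol 7.5). That table has three ratings:

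- **Probable**: reasonable timing; "Follows a known response pattern to the study drug and"; and the event "Cannot be reasonably explained by the known characteristics of the" subject's condition, or by other treatment.
- **Possible**: reasonable timing; "Follows a known response pattern to the study drug, but"; "Could have been produced by the subject's clinical state or by other therapies".
- **Unlikely**: "An AE for which sufficient information exists to indicate that the etiology is unrelated to the study drug", with another cause specified. A footnote again asks for a likely cause.

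There is no definite, unrelated or unassessable rating.

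Protocol 9.8.1 and SAP 8.3.1 plan the TEAE summary on a different scale: "By relationship to clinical trial treatment (definitely related, probably related, possibly related, unlikely related, unrelated". Both sections count a subject once, at the worst-case relationship category. Both also break down by relationship the SAEs, the AEs leading to death and the AEs leading to discontinuation.

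**The concern.** A causality scale for a drug with limited exposure in this disease should have a place for a reaction nobody has yet described. Table 2 appears to have none, because being already known is a condition of both ratings that mean drug-related. The plan itself allows for such reactions: Protocol 4.2 says that amyloid-related imaging abnormalities and their clinical consequences cannot be excluded, although nothing in study NTRP101-202 pointed to them clinically. Safety and tolerability are part of the primary objective.

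What is at stake is the set of tables broken down by relationship. If the definition gives no answer, investigators at about 30 sites must either set it aside or leave the rating open, and they need not do so in the same way. The three-against-five mismatch affects the same tables and applies to every AE, not only to new ones.

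**Working it through.** The plan gives no figure on this point, so the check is logical.

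**Step 1. Conditions.** Let T = reasonable timing, K = known response pattern, A = another cause could explain the event. From Table 2:

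- Probable = T and K and not A
- Possible = T and K and A
- Unlikely = sufficient information that the event is unrelated, and another cause named (so A is needed)

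**Step 2. All 2 × 2 × 2 = 8 combinations.**

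| T | K | A | Rating available |
|---|---|---|---|
| yes | yes | no | Probable |
| yes | yes | yes | Possible |
| yes | no | no | none |
| yes | no | yes | Unlikely, only if the evidence condition is met |
| no | yes | no | none |
| no | yes | yes | Unlikely, only if the evidence condition is met |
| no | no | no | none |
| no | no | yes | Unlikely, only if the evidence condition is met |

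One combination is Probable, one is Possible, three can be Unlikely only on positive evidence, and three have no rating: 1 + 1 + 3 + 3 = 8.

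The third row is the important one: plausible timing, new reaction, no other cause. It fails Probable and Possible on K and fails Unlikely because no other cause can be named. The fourth row is the next: a new reaction with a merely conceivable other cause cannot be Possible, and it is Unlikely only if there is enough information that the drug was not responsible.

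**Step 3. Does this depend on how Unlikely is read?** Its two conditions are not joined by an explicit *and*. If either one sufficed, the third row would still fail both, having neither evidence of unrelatedness nor another cause. The gap remains.

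**Step 4. Against Protocol 7.4.** There, pattern is one factor among several and every AE must be classified. In Table 2, pattern is necessary for both related ratings. The two sections cannot both be followed for the third row.

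**Step 5. Levels defined against levels tabulated.**

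| Protocol 9.8.1 and SAP 8.3.1 | Table 2 |
|---|---|
| definitely | no definition |
| probably | Probable |
| possibly | Possible |
| unlikely | Unlikely, defined as evidence of being unrelated |
| unrelated | no separate definition |

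Five levels less three defined leaves two without a definition. Because Table 2 describes Unlikely by evidence of unrelatedness, the last two rows cannot be separated. Counting at the worst-case level needs one ordered scale with every event on it. The missing-data rules under SAP 7.3 cover efficacy only, and SAP 8.3.1 does not say how to treat an AE without a relationship rating.

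**The case against.** The strongest reply is the judgment clause of Protocol 7.4: an investigator weighing all the factors could rate a new reaction Possible or Probable. That is likely to happen in practice and is a fair limit on the point. But the rating is still expressed through Table 2, so the investigator must depart from its definition, and others may not.

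Several stronger conclusions are tempting, and the documents do not support them.

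- *Related and unexpected are close to mutually exclusive, so expedited reporting fails.* Protocol 7.6.2 says "Any SAE that is serious, suspected to be related to investigational study drug and unexpected (SUSAR), will be promptly reported", but does not tie suspicion to a Table 2 rating. Under 7.5.1 an event is also unexpected if it "is not listed at the specificity or severity that has been observed", so a known reaction at greater severity can be both related and unexpected. Only a wholly new reaction type is affected. No passage equates a known pattern with listing in the Investigator's Brochure. SAEs go in within 24 hours regardless of causality, a pharmacovigilance physician or designee reviews relationship and expectedness (7.6.1), and unexpected SAEs go to the IRB with no relatedness condition (7.6.2).
- *Late new SAEs are no longer collected.* Up to 30 days after the last dose, causality is irrelevant. After that, 7.6 and 7.6.1 ask what the investigator considers or determines, again without citing Table 2. Section 7.6 also asks for unusual safety information even after a subject has finished.
- *New reactions are pushed into Unlikely, which lowers the bryostatin count.* Unlikely has conditions that such an event does not meet. The literal result is an event without a rating; how sites would resolve that is unknown.
- *The treatment-related TEAE rates in study 202 (16.7% placebo, 37.0% on 20 µg) measure the loss.* The causality definitions used in that study are not given, so these rates show nothing lost through this table.
- *The seizure in study 202 is an example.* It was among the events judged possibly or probably related, and whether it was a known pattern cannot be settled without the Investigator's Brochure.

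It is also true that TEAEs are compared between arms regardless of relationship, with separate SAE and discontinuation summaries. That protects the main safety comparison but not the relationship breakdowns.

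**Conclusion.** The point holds in a limited form. As written, Table 2 has no rating for a plausibly timed new reaction without another cause, and it does not allow Possible for a new reaction with a merely conceivable one. This conflicts with Protocol 7.4. Independently, Table 2 defines three of the five levels that Protocol 9.8.1 and SAP 8.3.1 will tabulate; one of the five has no definition and two cannot be separated.

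The consequence is inconsistent or missing relatedness ratings for wholly new reaction types, seen mainly in the relationship tables. Neither the number of events nor the direction of any difference between arms can be derived from the documents. The effect on expedited reporting is limited, and the overall TEAE and SAE summaries by arm are untouched.

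Two assumptions matter. The Table 2 conditions are taken as cumulative, as their connecting words indicate. The eCRF is taken to collect the Table 2 ratings; if it already offers five, the missing definitions remain the problem.

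**What to change.** 1. In Table 2, make the known response pattern a supporting feature of Probable and Possible, not a required condition.
2. State that an event with plausible timing and no established alternative cause is rated at least Possible.
3. Use one ordered set of relationship levels, each defined, in Table 2, the eCRF, Protocol 9.8.1 and SAP 8.3.1. Either define the two extra levels or drop them from the tables. The set should also place events with implausible timing and no named cause, the two remaining rows without a rating, which items 1 and 2 do not cover.
4. State in SAP 8.3.1 how an AE with no relationship rating is counted under the worst-case rule.

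The cost is one table edit, eCRF completion guidance and a few lines in the SAP. The downside is that somewhat more events will be rated related in both arms.

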7.5.1 Unexpected Adverse Event

An AE is considered “unexpected” if it is not listed in the Investigator’s Brochure (IB) or is not listed at the specificity or severity that has been observed. Unexpected refers to AEs that are mentioned in the IB as occurring with a class of drugs or as anticipated from the pharmacological properties of the drug, but are not specifically mentioned as occurring with the particular drug under investigation. However, an event that is more specific or more severe than described in the IB will be considered unexpected.

7.6 Reporting Adverse Events

The PI should instruct all subjects/caregivers on the procedure for reporting AEs/SAEs to the appropriate clinical site personnel. For each AE reported by parents/guardians, clinical site personnel should obtain all required information to complete the eCRF.

The PI or designee should document all AEs/SAEs in subjects’ source documentation and on the AE eCRF.

In addition to standardized reporting procedures, worsening or exacerbation of concurrent conditions in subjects will also be reported as AEs, and will follow the designated reporting format.

The following should be recorded with each SAE/AE:

- The nature of the AE, with a diagnosis wherever possible
- Date of event
- Assessment of intensity
- Is this an SAE?
- Relationship to study drug or trial-related procedures
- Action taken regarding study drug treatment
- Outcome

If the intensity of an already reported AE increases, then a new AE eCRF must be completed for that AE. The date of change would be included as the end date for the originally reported AE, and the start date for the new AE of greater intensity.

The clinical research associate is responsible for source document verification of all safety events.

If the clinical site becomes aware of an SAE, regardless of causality, within 30 days following the last administration of investigational product, the SAE should be recorded and reported immediately to the Sponsor. An SAE that occurs more than 30 days after the last dose will NOT be collected unless the PI considers that the event is related to the investigational product.

The sponsor should be informed if the PI becomes aware of any unusual safety information or any potential drug-related safety information, even after a subject completes the study

7.6.1 SAE reports

All SAEs, whether or not considered associated with study treatment or study-related procedures, must be reported on the eCRF immediately and no later than 24 hours after the site becomes aware of the event. Follow-up information must be provided promptly as requested.

The PI is obligated to provide as much information about the event as possible on the eCRF provided and as requested by the Sponsor or Medical Monitor.

In general, this will include a description of the SAE in sufficient detail to allow for a complete medical assessment of the case. The pharmacovigilance physician or designee will review the SAE including the SAE criteria, the relationship to study medication, the expected or unexpected assessment, and inform the Sponsor by phone and e-mail immediately.

The following AEs should also be reported to the Sponsor's designated Medical Monitor immediately:

- severe injection/infusion site reactions (ulceration or necrosis that is severe; operative intervention indicated)
- systemic hypersensitivity reactions
- myalgia

All additional follow-up evaluations must be reported by the site to the medical monitor, or designee, immediately after notification of the additional information.

An SAE will be followed until it resolves or reaches a clinically stable outcome. AEs/SAEs that have not resolved by study closure will be considered ongoing.

An SAE that occurs after the 30-day safety visit will NOT be collected unless the PI determines that the event is related to the investigational drug product.

7.6.2 Reporting to Regulatory Authorities

The PI, or designee, is responsible for informing the Institutional Review Board (IRB) of any unexpected SAEs, as well as any additional SAEs according to the IRB's policy.

Any SAE that is serious, suspected to be related to investigational study drug and unexpected (SUSAR), will be promptly reported to regulatory authorities by the Sponsor according to expedited reporting requirements. Subsequent relevant information after the initial submission of the (IND) Safety Report to the regulatory authorities will be submitted in a follow-up IND Safety Report to the regulatory authorities in the expedited period by the Sponsor.

7.7 Criteria for Withdrawal of Subjects

Subjects may be withdrawn from the clinical study for the following reasons:

- The PI believes withdrawal to be medically necessary or in the best interest of the subject
- Noncompliance with the protocol as judged by the PI (requires discussion with the Sponsor)
- Subjects who are enrolled in violation of inclusion and/or exclusion criteria
- An AE that presents an unacceptable consequence or risk to the subject as judged by the PI, Sponsor or the Medical Monitor
- Lost to follow up
- Withdrawal of consent
- Subject is unblinded

Subjects may voluntarily discontinue their participation in the study at any time without prejudice to further treatment.

7.8 Criteria for Permanent Discontinuation of Study Drug

Study drug treatment may be discontinued for the following reasons:

- if sponsor or regulatory authorities discontinue study

- if the PI believes that discontinuing treatment is in the best interest of the subject

7.9 Study Discontinuation

Neurotrope has the right to discontinue this clinical study at any time. The PI has the right to discontinue participation in this clinical study at any time for any reason. Clinical study site discontinuation should only occur after mutual consultation between the PI and Neurotrope.

Should the clinical study be discontinued prematurely, all subjects should be brought in for early termination procedures as outlined for the 30-day Follow-up visit. All clinical study materials should be returned to Neurotrope or designee.

8 SAFETY MONITORING

An Independent Safety Monitor will provide consultation to Neurotrope to assess the implementation and progress of study NTRP101-203 and will review accumulating trial data to monitor the safety of bryostatin administered to patients with AD. Safety data will be reviewed when 30 subjects have received four doses of study drug, followed by additional safety analyses when 60 subjects have received a similar number of doses. Medical decisions relevant to this study will be made by the Sponsor in consultation with the Primary Investigator, Medical Monitor and Statistician.

Prior to each safety review, a cut-off date for the data to be provided will be established by the Sponsor in consultation with the WCT Supporting Biostatistician. The format and content of data listings will be approved by the Supporting Biostatistician. Data reports will be provided as partially blinded displays (e.g., data is grouped by unblinded treatment using "Group A, B" to indicate treatment). The identity of each group will be available to the safety reviewer via the Supporting Statistician.

Data review documents, safety data tables and listings, will be provided to the Independent Safety Monitor at least 7 business days prior to scheduled reviews. Serious Adverse Events (SAEs) reported during the 7 days before the scheduled review and therefore not included in the provided documentation will be provided by the WCT Drug Safety Manager as soon as possible before the review date. The reviews of the safety data will be summarized for the overall subject group only and will not be separated by treatment groups.

